Acute Oroantral Communication Closure: Resorbable Collagen Membrane vs. Buccal Advancement Flap Outcomes: A Clinical Trial

PCN/0022/KB1/94/20/21

12.02.2021

Study Protocol and Statistical Analysis Plan

Protocol Overview and Rationale

This investigator-initiated, prospective, non-randomized, parallel-group clinical study was designed to compare the clinical effectiveness and early radiographic healing associated with two surgical techniques for closure of acute oroantral communication (OAC) diagnosed within 24 hours after extraction of posterior maxillary teeth. The study was conducted at the Department of Dental Surgery, Faculty of Medical Sciences in Zabrze, Medical University of Silesia. The protocol was approved by the Institutional Review Board (PCN/0022/KB1/94/20/21), and all participants provided written informed consent prior to enrollment.

The study hypothesis was that minimally invasive closure using a resorbable heterogeneous collagen membrane would better preserve soft tissue architecture and reduce postoperative morbidity compared with the conventional Rehrmann buccal advancement flap, while maintaining comparable early bone healing.

Study Population and Enrollment

Consecutive adult patients presenting with acute OAC within 24 hours following extraction of a maxillary posterior tooth were screened for eligibility according to predefined inclusion and exclusion criteria. Twenty-four patients were enrolled; twenty completed the full 90-day follow-up and were included in the final analysis. The mean defect diameter was 3.5 ± 1.0 mm (range 2 to 5 mm), verified clinically and with limited-field CBCT on day 0.

Interventions and Standardization

Participants were assigned to one of two parallel treatment arms based on a predefined clinical protocol and the availability of the membrane technique at the time of treatment. Formal randomization and allocation concealment were not implemented.

All surgical procedures were performed by the same experienced oral surgeon to minimize operator-related variability. Preoperative preparation, socket debridement, smoothing of sharp bony margins, antibiotic prophylaxis, sinus precautions, analgesic recommendations, and follow-up schedules were standardized across both groups.

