Experimental arm: closure using submucosal placement of a resorbable heterogeneous collagen membrane (Creos Xenoprotect) stabilized with horizontal mattress sutures following limited mucoperiosteal elevation without vertical releasing incisions.

Control arm: closure using the classical Rehrmann buccal advancement flap involving trapezoidal full-thickness mucoperiosteal flap elevation with vertical releasing incisions and periosteal releasing incision to permit tension-free coronal advancement.

Follow-up Schedule and Data Collection

Clinical assessments were conducted at baseline (day 0) and on postoperative days 1, 7, 14, and 90. The final radiographic assessment using limited-field CBCT was performed at baseline and at 90 days.

Clinical measurements (vestibular depth, keratinized gingiva width, alveolar socket dimensions) were performed using a calibrated WHO periodontal probe by an independent

examiner blinded to the surgical procedure. Examiner calibration was performed prior to study initiation using repeated measurements in a subset of patients.

Radiographic measurements and region-of-interest (ROI) density analyses were conducted by two trained investigators using standardized protocols in Romexis (v6.4) and ImageJ (v1.53k). Discrepancies were resolved by consensus.

Outcome Measures

Primary endpoint:

- Change in vestibular depth from baseline to 90 days.

Secondary endpoints:

- Change in keratinized gingiva width.
- Change in alveolar socket dimensions.
- Postoperative pain intensity measured with the Visual Analogue Scale (VAS) at days 1, 7, and 14.
- Incidence of postoperative complications (swelling, hematoma, epistaxis, wound dehiscence, persistent communication, fistula formation, clinical sinusitis).
- Normalized bone density at the surgical site derived from CBCT.

Radiographic Density Methodology

Because CBCT gray values are not directly equivalent to absolute Hounsfield Units, density measurements were normalized to adjacent cortical bone within the same scan to reduce inter-individual variability and acquisition-related bias. Regions of interest were placed at three standardized vertical levels of the alveolus (crestal, mid-alveolar, and apical). The arithmetic mean of normalized values was used for statistical analysis.

Statistical Analysis Plan

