All analyses were performed using STATISTICA version 13.0. Continuous variables are presented as mean \pm standard deviation. Categorical variables are presented as counts and proportions.

Assumption testing:

- Normality assessed with the Shapiro–Wilk test.
- Homogeneity of variance assessed with Levene’s test.

Between-group comparisons:

- Independent-samples t test for normally distributed variables with equal variances.
- Mann–Whitney U test when parametric assumptions were violated.

Multiplicity control:

The primary endpoint retained a two-sided alpha of 0.05. Because multiple secondary endpoints were analyzed, Bonferroni correction was applied for secondary comparisons, and these results were interpreted as supportive.

Handling of missing data:

Only participants who completed the 90-day follow-up were included in the final per-protocol analysis. No imputation of missing values was performed.

Power considerations:

Given the final sample size ($n = 20$), the study was adequately sensitive for detecting large between-group differences in soft tissue outcomes but underpowered for moderate radiographic density effects. Therefore, CBCT density findings were prespecified as exploratory.

Bias Control Measures

- Single experienced surgeon to reduce procedural variability.
- Independent blinded clinical assessor.
- Dual-investigator radiographic analysis with consensus resolution.
- Standardized postoperative management in both arms.
- Objective probe-based measurements at predefined time points.

Safety Monitoring

Participants were monitored at each follow-up visit for adverse events, including infection, dehiscence, hematoma, epistaxis, persistent OAC, fistula formation, and signs of maxillary sinusitis. All complications were recorded prospectively. No serious adverse events related to the interventions were reported.

Ethical Considerations

The study complied with the Declaration of Helsinki and applicable institutional requirements. Participation was voluntary, and patients could withdraw at any time without affecting their treatment. Data confidentiality was maintained throughout the study.

Protocol Limitations

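### CBCT density is listed as a secondary endpoint but also called exploratory, so membership of the Bonferroni family is inconsistent; give density one status and use Holm

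*Combined protocol and SAP*

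**What the plan says.** - **Outcome Measures** lists five secondary endpoints: keratinized gingiva width, alveolar socket dimensions, pain, complications and density. The density entry reads "Normalized bone density at the surgical site derived from CBCT". The pain entry reads "Postoperative pain intensity measured with the Visual Analogue Scale (VAS) at days 1, 7, and 14". The complications entry names seven events.
- **Statistical Analysis Plan, Multiplicity control:** "The primary endpoint retained a two-sided alpha of 0.05". For the rest, "Bonferroni correction was applied for secondary comparisons, and these results were interpreted as supportive". The number of comparisons and the adjusted threshold are not given.
- **Statistical Analysis Plan, Power considerations** argues from the final number analysed (20) that moderate density effects could not be detected, and concludes: "Therefore, CBCT density findings were prespecified as exploratory".
- **Study Population and Enrollment:** of 24 enrolled, "twenty completed the full 90-day follow-up and were included in the final analysis".
- **Protocol Limitations** closes with the statement that the SAP was settled before the database was locked and the outcomes were analysed.

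**The concern.** A Bonferroni threshold is fixed only when its family is fixed. The endpoint list and the multiplicity rule together put density inside the family, and the power section takes it out. No sentence reconciles them, so two analysts following the same plan could use different thresholds for keratinized width, socket dimensions, pain and complications. Lower postoperative morbidity is part of the study hypothesis, and both pain and complications are judged against this threshold.

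The ground given for the exploratory label is a second difficulty. It is the number of completers, which cannot be known until the last patient reaches day 90. A status derived from that number was not set at design, although the word used suggests that it was.

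Finally, single-step Bonferroni is not the best use of a limited alpha. Holm controls the same familywise error and never rejects fewer hypotheses.

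**Working it through.** The plan gives no adjusted alpha or numerical power, so there is no figure to reproduce.

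**Inputs**
- From the documents: 20 analysed; five secondary endpoints, one of them density; Bonferroni for secondary comparisons.
- Assumed: family alpha 0.05, two-sided; 10 per arm, because the arm sizes are not given and "Formal randomization and allocation concealment were not implemented" (8/12 and 6/14 also tried); Fisher's exact test for complications, because no categorical test is named; independent endpoints in the simulations.

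**Step 1. Threshold and detectable difference**

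Threshold = 0.05/m. Power is that of the two-sided two-sample t test from the noncentral t distribution, with n1 + n2 − 2 = 18 degrees of freedom and noncentrality d × √(n1·n2/(n1 + n2)) = d × √(100/20) = 2.236d. The table solves for the d that gives 80% power.

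| Counting rule | Density in: m, threshold, d | Density out: m, threshold, d |
|---|---|---|
| One test per endpoint | 5, 0.0100, 1.69 | 4, 0.0125, 1.64 |
| Pain by day | 7, 0.0071, 1.76 | 6, 0.0083, 1.73 |
| Pain by day and each complication | 13, 0.0038, 1.89 | 12, 0.0042, 1.87 |

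Only the first row follows the endpoint list as written. The other two show what would happen if tests were split. Removing density gains 0.02 to 0.05 SD in any row. With no correction the detectable difference is 1.32 SD. In the first row, 8/12 gives 1.72 and 1.67 SD, and 6/14 gives 1.84 and 1.79 SD.

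**Step 2. Can density's status change a result?**

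For 6/10 against 0/10, two-sided Fisher p = 2 × C(10,6)/C(20,6) = 2 × 210/38,760 = 0.0108. This exceeds 0.0100 and is below 0.0125. Any p value between those limits behaves the same way, whatever the test.

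**Step 3. Source of the low power (10 per arm)**

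At 0.8 SD, power is 39.5% with no correction and 17.2% at m = 5. At 2.0 SD it is 92.9% at m = 5 and 85.4% at m = 13.

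**Step 4. Holm against Bonferroni**

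Average power over the endpoints with a true effect, by simulation:

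| True effects | Bonferroni | Holm |
|---|---|---|
| All five at 1.3 SD | 52–53% | 65% |
| Four at 1.3 SD, density null | 53% | 60% |
| Three of five at 1.5 SD | 68% | 73% |
| One of five at 1.5 SD | 68% | 68% |
| Two of five at 0.8 SD | 17% | 18% |

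The gain runs from almost nothing to about 12 to 13 percentage points. The first row is the most favourable case, because it gives density a large effect although the hypothesis expects comparable bone healing. With density out and the other four all at 1.3 SD, Holm reaches 68%.

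**The case against.** The strongest reply is that this is a labelling slip with little consequence. Bonferroni is valid, secondary results are described as supportive, and bone findings are called hypothesis-generating. Removing density barely moves the power. All of this stands, and it limits the severity. It does not remove the contradiction about which threshold applies.

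Three stronger readings are tempting, and the documents do not support them.

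- **That there are at least 13 corrected tests, with a threshold of 0.0038.** The count would be 1 + 1 + 3 + 7 + 1. Nothing says that pain is tested separately on each day or complications event by event. The multiplicity sentence gives multiple secondary endpoints as its reason, which favours five. No categorical test is named, so complications may be purely descriptive. Without them, the same count gives 1 + 1 + 3 + 1 = 6. Thirteen is one possible reading and not a minimum.
- **That the correction makes real effects nearly undetectable.** Step 3 shows that power is poor for effects near 0.8 SD even without correction, and good at 2.0 SD with it. The main limit is 20 patients. Splitting complications does not explain the binary case either: against 0/10, significance needs 7/10 at m = 5 as well as at m = 13.
- **That density was downgraded after its results were seen.** The document says that the SAP was settled before outcome analysis, and the number of completers can be known before then. The text shows only that the status relied on a number unavailable at design.

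**Conclusion.** The concern holds as an internal contradiction of minor severity. Density is inside the corrected family by the endpoint list and outside it by the power section. On the per-endpoint count this leaves the threshold at either 0.010 or 0.0125, and a result such as 6/10 against 0/10 changes side. The threshold would be lower if pain days or complications were tested separately, which the plan does not say.

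Calling the exploratory status prespecified is not supported as a statement about the design stage. It is compatible with a decision made before outcomes were analysed.

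Holm is a better procedure than the one chosen, by an amount that depends on how many endpoints truly differ. The choice of Bonferroni is not an error. The power figures rest on the assumed 10 per arm, the Fisher example also on that test being used, and the Holm gains also on independent endpoints. The threshold conflict needs only a family alpha of 0.05 and the per-endpoint count.

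**What to change.** 1. Take CBCT density off the secondary list and place it under an exploratory heading, outside the correction, reported by an estimate and 95% CI.
2. State that this status was set once the final number of patients was known and before outcome analysis, and drop the claim of prespecification.
3. List the remaining secondary comparisons, state their number and the family alpha, and name the test for complications if they are tested.
4. Apply Holm to that list: order the p values and compare them in turn with 0.05/m, 0.05/(m − 1) and so on, stopping at the first failure.

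The cost is SAP wording and a short recalculation, with no new data. If outcomes have already been analysed, both changes can only make the remaining tests easier to pass. They should then be disclosed as later changes, with the Bonferroni results shown alongside.

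Reducing pain to one average over the three days, or complications to one any-event composite, is optional. An average can dilute an early pain effect, and a composite weighs swelling equally with a fistula. Neither is needed to resolve the contradiction.

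### Limiting every analysis to day-90 completers also drops any early pain scores and complications recorded for the 4 of 24 patients who did not complete, which can bias the morbidity comparison in an unknown direction

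*Combined protocol and SAP*

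**What the plan says.** Under Handling of missing data, the SAP states: "Only participants who completed the 90-day follow-up were included in the final per-protocol analysis". It adds: "No imputation of missing values was performed". Study Population and Enrollment gives the numbers: "Twenty-four patients were enrolled; twenty completed the full 90-day follow-up and were included in the final analysis". No other analysis set is defined: there is no safety set, no available-case analysis of the early visits and no sensitivity analysis.

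Two secondary endpoints do not depend on day 90. Outcome Measures lists "Postoperative pain intensity measured with the Visual Analogue Scale (VAS) at days 1, 7, and 14" and "Incidence of postoperative complications (swelling, hematoma, epistaxis, wound dehiscence, persistent communication, fistula formation, clinical sinusitis)". The visit schedule reads: "Clinical assessments were conducted at baseline (day 0) and on postoperative days 1, 7, 14, and 90". Safety Monitoring adds: "All complications were recorded prospectively".

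Morbidity is part of the study hypothesis, which expects the membrane to "reduce postoperative morbidity compared with the conventional Rehrmann buccal advancement flap". Protocol Limitations does not mention attrition.

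**The concern.** The rule selects patients on something that happens after treatment. A patient with a painful recovery, a complication or a failed closure may be more likely, or less likely, to return at day 90 than one who healed without trouble. If return depends on the outcome and does so differently by arm, the completer comparison of pain and complications no longer describes the patients who had the two operations. A patient whose closure fails and who does not come back leaves both the numerator and the denominator of the complication rate.

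No visit is scheduled between day 14 and day 90, so such a loss could go unseen. Allocation was not randomized, and selective loss would add to whatever imbalance the arms already had. At stake are the morbidity part of the hypothesis and the closure-failure rate, in a study small enough for four patients to matter. For endpoints measured only at day 90 the completer restriction is largely unavoidable. For pain to day 14 and for complications it is not.

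**Working it through.** Closure failure is used here as shorthand for persistent communication or fistula.

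**Inputs from the documents.** 24 enrolled and 20 analysed (Study Population and Enrollment); pain at three visits and complications as an incidence (Outcome Measures). Arm sizes, the arm split of the losses, their timing and reasons, and event counts are not given. Everything below that needs them is an assumption.

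**1. The plan's own figure.** 24 − 20 = 4 patients excluded; 4/24 = 16.7%. The n = 20 in the SAP agrees. The power statement is qualitative, so there is no power figure to reproduce.

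**2. Pain scores at risk of exclusion.** At most 4 × 3 = 12 of 24 × 3 = 72 scores (16.7%). This ceiling applies only if all four had surgery and attended all three early visits.

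**3. Closure failure overall.** Suppose no completer had a failure. The completer analysis would report 0/20 (exact 95% upper limit 16.8%). Depending on what happened to the four, the count among all enrolled lies between 0/24 and 4/24 = 16.7% (exact 95% CI 4.7% to 37.4%).

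**4. Closure failure by arm.** Assume 10 completers per arm and none with a failure. Each row gives the highest possible risk in each arm for one split of the losses:

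| Lost, membrane / flap | Highest membrane risk | Highest flap risk |
|---|---|---|
| 0 / 4 | 0/10 = 0% | 4/14 = 28.6% |
| 1 / 3 | 1/11 = 9.1% | 3/13 = 23.1% |
| 2 / 2 | 2/12 = 16.7% | 2/12 = 16.7% |
| 3 / 1 | 3/13 = 23.1% | 1/11 = 9.1% |
| 4 / 0 | 4/14 = 28.6% | 0/10 = 0% |

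The exact 95% CI is 2.1% to 48.4% for 2/12 and 8.4% to 58.1% for 4/14. The table is symmetric: nothing in the documents favours one arm.

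**5. Effect on a comparison.** Take purely illustrative completer counts of 0/10 (membrane) and 5/10 (flap) with any complication: difference −50 points, Fisher p = 0.033 before Bonferroni. Add two lost patients to each arm:

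- both membrane losses had an event and neither flap loss did: 2/12 v 5/12, −25 points, p = 0.37;
- neither membrane loss had an event and both flap losses did: 0/12 v 7/12, −58 points, p = 0.005.

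**6. Pain.** Let m of N patients in an arm be excluded, with a mean score D above the completers (D may be negative). The mean over all N is [(N − m) × completer mean + m × (completer mean + D)] / N = completer mean + (m/N) × D. The arm mean therefore moves by 0.17 × D for 2 of 12 and 0.29 × D for 4 of 14. D is not known. For D of 1, 2 or 3 points the shift is 0.17, 0.33 or 0.50 in the first case and 0.29, 0.57 or 0.86 in the second.

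**The case against.** The strongest reply has four parts.

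- **The data may not exist.** The documents count patients enrolled, not operated on, and give no timing for the losses. A patient who left before day 7 has at most one pain score. A reader might infer that a full set of early data was collected on four treated patients and then thrown away. The text does not support that. It supports only that whatever was recorded falls outside the stated analysis set.
- **Safety reporting may be wider.** Safety Monitoring speaks of participants at each follow-up visit and does not limit itself to completers. But it sets no denominator for the complication endpoint either, and its closing statement concerns only serious, related events. The completer rule, stated without exception, is the only rule there is.
- **The endpoints are secondary.** They are Bonferroni-corrected and treated as supportive. This lowers the stakes, but correcting alpha does not remove selection bias, and morbidity stands in the hypothesis.
- **Reanalysis cannot recover everything.** A failure that occurs after a patient's last visit was never recorded. This stands, and it is why bounds are needed as well as a wider analysis set.

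Two further inferences should be resisted. One is that the rule hides failures in the membrane arm in particular; the arm of the losses is not given, and the bounds run equally both ways. The other is that the per-protocol label is itself a serious error. The set is openly defined, and the label matters only because the definition rests on completion and gives no adherence criterion.

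**Conclusion.** The concern holds as a fault in a stated rule. The SAP makes day-90 completion the condition for entering the analysis of endpoints that do not need it, and this can bias the comparison of pain and complications. Four of 24 enrolled patients (16.7%) are affected. With no failures among completers, the overall closure-failure risk among the enrolled could be anything from 0% to 16.7%. In a single arm it could be up to 28.6% if all four losses fell there.

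The arm figures rest on an assumed 10/10 split of completers, and the event counts are illustrations rather than trial results. Whether bias occurred, in which direction and by how much cannot be determined from the documents. The wording of the rule is certain; actual loss of recorded data is only possible.

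**What to change.** Change the SAP as follows:

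- **Pain:** at each of days 1, 7 and 14, analyse all enrolled patients who received a study procedure and have a score. A repeated-measures model is an option, not a requirement.
- **Complications and closure failures:** report them for all such patients by technique received, counting any event recorded at any visit whether or not the patient attended at day 90. State the denominator.
- **The 4 losses:** report arm, timing, reason and last-known closure status, and whether each had surgery.
- **Bounds:** give best- and worst-case results for closure failure by arm, since events after a patient's last visit cannot be recovered.
- **Completer set:** keep it for the 90-day change in vestibular depth and for CBCT density. Use it for keratinized gingiva width and socket dimensions where these are analysed at day 90; the plan names no time point for these two. Call it a completer analysis.

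If outcomes have already been analysed, date the change and show the results in both sets.

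The cost is SAP wording and a rerun on data already recorded, with no new patients or visits. Complication rates may move in either direction.

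### The primary endpoint is missing for 4 of 24 patients and is analysed in completers only, with no sensitivity analysis, so a result close to significance could be fragile without the reader being able to tell

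*Combined protocol and SAP*

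**What the plan says.** Study Population and Enrollment reports: "Twenty-four patients were enrolled; twenty completed the full 90-day follow-up and were included in the final analysis". Outcome Measures defines the primary endpoint as "Change in vestibular depth from baseline to 90 days". Under Handling of missing data, the SAP says: "Only participants who completed the 90-day follow-up were included in the final per-protocol analysis. No imputation of missing values was performed".

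Under Multiplicity control, "The primary endpoint retained a two-sided alpha of 0.05". The comparison is an independent-samples t test, with Mann–Whitney U as the fallback. Power considerations gives no effect size, SD or power figure, only that "the study was adequately sensitive for detecting large between-group differences in soft tissue outcomes".

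The document describes no all-enrolled, best/worst-case, tipping-point or other missing-data analysis. It does not state the arm sizes, or the arm and reason for each of the four losses. Protocol Limitations covers allocation, sample size, length of follow-up and CBCT density, but not attrition. Its hypothesis-generating caveat is attached to the bone findings, not to the primary endpoint.

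**The concern.** A completers-only comparison estimates the effect in everyone enrolled without bias only if the missing changes match the observed ones on average within each arm, or if the departures cancel between arms. The plan neither states nor examines that condition.

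There are reasons to doubt it. Day 90 is the only scheduled visit after day 14, and participation could be ended at any time. A patient may stay away because healing went well or because it went badly. The two procedures differ in invasiveness, so the pattern of loss could differ by arm. Allocation was not randomized, and none of the listed bias controls deals with loss to follow-up.

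At stake is the only test held at the full 0.05 level. With about 10 patients per arm, four unobserved outcomes can move the estimate by a sizeable fraction of its standard error. The planned output would not show by how much.

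**Working it through.** **Inputs from the documents.** 24 enrolled and 20 analysed; continuous endpoint at day 90; two-sided alpha 0.05; t test. Missing: 24 − 20 = 4, and 4/24 = 16.7%. The plan states no numerical power or effect size, so there is no figure of its own to reproduce.

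**Assumptions.** 10 completers per arm; within-arm SD = 1, so everything is in SD units; observed difference D varied; the four losses split 4/0 or 2/2. Non-completers are taken to have no day-90 value.

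**Completer test.** SE = √(1/10 + 1/10) = 0.447, with 18 df. Significance needs D ≥ 2.101 × 0.447 = 0.94. For 80% power the true difference must be about 1.32. For D = 1.2, t = 1.2/0.447 = 2.68 and p = 0.015.

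**Bias.** Let π be the missing share in an arm and δ the departure of its missing mean from its completer mean. The all-enrolled difference then differs from the completer difference by π₁δ₁ − π₂δ₂.
- Losses 4/0, departure of 1 SD: 4/14 = 0.29 SD.
- Losses 2/2, opposite departures of 1 SD: 2/12 + 2/12 = 0.33 SD.
- Losses 2/2, same departure in both arms: 2/12 − 2/12 = 0, no bias.

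**Tipping point by multiple imputation.** The missing changes were drawn from own-arm data and shifted against the observed effect, then combined by Rubin's rules with small-sample df. For D = 1.2, at shifts of 0, 0.5, 0.75 and 1.0 SD:
- losses 4/0: p about 0.02, 0.04, 0.055, 0.08;
- losses 2/2, opposite shifts: p about 0.02, 0.04, 0.066, 0.10.

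A cruder calculation adds the four back at shifted means and treats them as if observed. It ignores imputation uncertainty and so makes the result look sturdier. Smallest shift that takes p above 0.05, by both methods:

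| Observed D | Completer p | Multiple imputation | Added back as if observed |
|---|---|---|---|
| 1.0 SD | 0.038 | well below 0.5 SD | 0.52–0.54 SD |
| 1.2 SD | 0.015 | about 0.6–0.7 SD | 0.99–1.06 SD |
| 1.5 SD | 0.0035 | about 1.2–1.5 SD | 1.61–1.76 SD |
| 2.0 SD | 0.0003 | about 2.3–2.6 SD | 2.5–2.8 SD |

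**A concrete benchmark.** Suppose all four losses are in the membrane arm and they average the control mean. Even by the cruder method, p becomes 0.11 at D = 1.0, 0.066 at 1.2, 0.030 at 1.5 and 0.0095 at 2.0.

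**The case against.** A reader might infer that the trial's primary result is fragile and is being presented as firm. The documents do not support that. They give no vestibular-depth result, SD, arm sizes or arm of loss, and the table shows the worry fading as the observed difference grows. The plan claims sensitivity only to large soft-tissue differences. If the observed difference is 2 SD or more, four missing patients are unlikely to overturn it.

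A reader might also infer that the analysis is valid only if the missing patients would have changed exactly as the completers in their own arm did. That is too strong. Equal departures with proportionate losses cancel, and the opposite-shift 2/2 case is deliberately adverse.

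The tipping figures depend on method as well as on D. At 1.2 SD they run from about 0.6 to about 1.06 SD, so none should be read as exact. With about 10 observed values per arm, imputation adds little information, and a simple shift table would carry most of the message.

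The plan is also open about whom it analyses. It labels the analysis per-protocol, says that nothing was imputed, and acknowledges the small sample and the lack of randomization.

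All of this stands and limits the claim. It does not remove the gap: the general caveats say nothing about the four missing patients, and a reader cannot tell from the planned output which row of the table applies.

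**Conclusion.** The concern holds in conditional form. The outcome of 16.7% of enrolled patients is left out of the primary analysis, and the plan offers no way to judge the effect of that. The bias depends on differential departure between arms: 0.29 to 0.33 SD for each 1 SD of departure in the two adverse patterns, against a standard error of 0.45 SD.

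A difference just past significance (about 0.94 to 1.3 SD) could be overturned by departures that cannot be ruled out from the documents. One of 2 SD or more would be robust. These sizes rest on an assumed 10/10 split of completers, roughly normal changes and the loss patterns shown. Nothing here establishes that the actual result is fragile. The added analysis could confirm it as readily as weaken it. This is a worthwhile, inexpensive improvement, not a flaw that invalidates the primary comparison.

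**What to change.** Keep the completer comparison as the main result. Replace the no-imputation statement with a shift (tipping-point) sensitivity analysis of the primary endpoint in all 24 patients:

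- Impute the four day-90 changes from own-arm data, using baseline vestibular depth if feasible.
- Shift the imputed values separately by arm over a stated range in mm. The range must include the case where each missing patient takes the other arm's mean.
- Tabulate the estimate, confidence interval and p value at each shift, and give the smallest shift that takes p above 0.05.
- Report the arm and reason for each of the four losses, and add attrition to Protocol Limitations.
- State the rule in advance: if significance is lost within the stated range, the primary conclusion is worded as conditional on the missing-data assumption.
- The SAP says it was completed before the database was locked, but it is written in the past tense and reports completion counts. If outcomes are already known, label this analysis post hoc.

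The cost is SAP wording and a few hours of analysis, with no new data. The downside is that the primary result may have to be reported as less robust.
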